2 ANALYTICAL PLAN

2.1 General Overview of Analyses

2.1.1 General Statistical Methods

Descriptive summary statistics including number of patients, mean, standard deviation, median, and range (minimum, maximum) for continuous variables, and counts and percentages for categorical variables will be used to summarize most data. All statistical tests will be conducted using 2-sided tests with 5% Type I error rate unless otherwise stated.

PK parameters will be summarized using number of patients, mean, standard deviation, coefficient of variation (CV), geometric mean, median, minimum, and maximum.

All analyses and tabulations will be performed using SAS® Version 9.2 or higher and Phoenix/WinNonlin version 6.1 or higher on a PC platform.

A separate analysis for on-treatment period might be provided if deemed necessary.

Pooled groups:

Patients who are placebo-treated will be pooled and analyzed as a single placebo group.

Patients who are ISIS 416858-treated may be pooled and summarized as the ISIS 416858 total group.

Baseline definition:

Unless otherwise specified, baseline for all safety laboratory results will be defined as the last non-missing measurement prior to the first dose. For post-dialysis Blood Urea Nitrogen (BUN) measures for Urea Reduction Ratio (URR) determination, post-dialysis baseline will be defined as the last non-missing post-dialysis measurement prior to the first dose

Analytical visits:

All post-baseline data will be summarized according to the visit windows in the table below. For patients who have multiple visits within a window, the average will be used in the summary for continuous variable and the worst case result will be used for categorical variable.

Table I Visit window for Clotting

Analysis visit	Visit window
Screening	<1
Baseline	last non-missing measurement prior to the first dose
Day8	[2, 11]
Day 15	[12, 21]
Day29	(22, 35]
Day43	[36, 49]
Day 57	[50, 63]
Day71	[64, 77]
Day 85	[78, 91]
Day99	(92, 105]

Day 113	[106, 116)
Day 120	[117, 126)
Day 134	(127, 140)
Day 148	(141, 154)
Day 162	[155, 168)
Day 176	[169, 182]
Day 190	(183, 196]
Day 204	[197, 210]
Day 218	[211, 224]
Day 232	[225, 238]
Day 246	(239, 252]
Day 260	[253, 266]

Table 2 Visit window for Vital Signs

Analysis visit	Visit window
Baseline	last non-missing measurement prior to the first dose
Day 5	(2, 6)
Day 8	[7, 9]
Day 12	[10, 13]
Day 15	[14, 17]
Day 22	[18, 25)
Day 29	[26, 32)
Day 36	[33, 39)
Day 43	[40, 46]
Day 50	[47, 53]
Day 57	[54, 60]

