2.3 Safety Analyses

Safety analyses will be based on the safety population. Safety summary tables will be presented by treatment group and ISIS 416858 total.

2.3.1 *Exposure*

Treatment duration, time on study, number of doses and amount and total volume of Study Drug (ISIS 416858 or placebo) received will be summarized by treatment group and ISIS 416858 total.

The treatment duration (days) for each patient is defined as last dose date - first dose date +1.

The time on study will be defined as the total number of days a patient is known to be followed on study calculated as follows:

$$\text{Time on study} = \text{Last date on study} - \text{Date of first dose} + 1.$$

Where the last date on study is defined as the date of the latest visit with evaluation, or time of death from all available data for a given patient. Visits with refused or unable to contact are not visits with evaluation.

The amount of Study Drug received (mg) for each patient is defined as the total volume (mL) administered from the 200 mg/mL stock solution.

2.3.2 *Compliance*

Percentage of compliance will be calculated and summarized by treatment groups and ISIS 416858 total.

$$\text{Study drug compliance} = 100 \times (\text{Total number of doses with injections given} / \text{Total number of doses with injections expected}).$$

If a patient discontinued the study treatment, the total number of doses with injections expected is counted, per the schedule of injections, up to the last attended study visit during the treatment period.

2.3.3 *Adverse Events*

The treatment emergent adverse events (TEAE) are defined as those AEs that occurred after dosing and those existing pre-dose AEs that worsened post-dose during the study.

The most conservative approach will be used to determine if the event occurs during the treatment or follow-up periods:

- AEs that have onset dates or resolution dates prior to the first study treatment dates will be considered to have occurred prior to the study period. If the onset or resolution date

of an AE is a partial date with only month or year available or complete missing, then the event is assumed to be within the study period unless the year is prior to the year of the first study treatment date, or if in the same year, the month is prior to the month of the first study treatment date.

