Local cutaneous reaction at injection site (LCRJS) is defined as (A) moderate or severe Injection Site Erythema, Swelling, Pruritus, Pain or Tenderness that started on the day of injection, persisted for at least two days; or (B) any AE at the Study Drug injection site, regardless of severity, that leads to discontinuation of study drug, where AE at the Study Drug injection site is the principal reason for discontinuation.

LCRIS will be summarized using the MedDRA coding system, by preferred term. Patients with moderate, severe and any LCRIS will also be summarized. Discontinuations due to AE at the injection site will be summarized separately.

Percentage of injections leading to LCRIS will be summarized by preferred terms and overall using the descriptive statistics. Additionally, percentage of Study Drug injections leading to LCRIS will be summarized by the moderate, severe severity and overall discontinuation of study drug due to AE at Study Drug injection site.

Percentage of Study Drug injections leading to LCRIS will be calculated as follows for each subject: (A/B)*100, where A=number of Study Drug injections with a LCRIS, and B=total number of Study Drug injections. Doses that are split across multiple Study Drug injections are counted as a single injection.

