2.3.3.2 Flu-like Reactions

Flu-like reactions (FLRs) will also be summarized using the MedDRA coding system, by preferred term.

Flu-like reactions are defined as either (A) flu-like illness or (B) Pyrexia or feeling hot or body temperature increased, plus at least two of the following: Chills, Myalgia, and Arthralgia, starting on day of injection or the next day.

Percentage of injections leading to flu-like reactions will be summarized using the descriptive statistics.

Percentage of the injections leading to flu-like reactions will be calculated as follows for each subject: (A/B)*100, where A=number of injections leading to flu-like reactions, and B=total number of injections.

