2.3.3.3 Bleeding

Major bleeding (MB) is defined as one of the following:

1. Fatal bleeding
2. Symptomatic bleeding in a critical area or organ, such as intracranial, intraspinal, intraocular, retroperitoneal, intraarticular if in a major joint, or pericardial, or intramuscular with compartment syndrome
3. Clinically overt bleeding leading to transfusion of units of packed red blood cells or whole blood or a fall in hemoglobin of 20 g/L(1.24 mmol/L) or more within 24 hours

Clinically relevant non-major bleeding (CRNMB) is defined as overt bleeding not meeting the criteria for major bleeding but that resulted, for example, in medical examination, intervention, or had clinical consequences for a patient.

Minor bleeding:

All other acute clinically overt bleeding events not meeting the criteria for either major or clinically relevant non-major bleeding will be classified as minor. Minor bleeding will be further categorized as injection site and non-injection site bleeding events.

The incidence of any bleeding event after first dose of study drug will be summarized by treatment group for the Safety Population for all bleeding events except minor bleeding at the injection site. Minor bleeding at the injection site will be summarized separately. The summary will include the following outcomes:

- MB
- CRNMB
- Minor bleeding (Non-injection site and injection site events)
- Combination of MB and CRNMB (with either MB or CRNMB)

The cumulative rate of first major bleeding events after first dose of study drug will be displayed using Kaplan-Meier curves for the safety population. Patients without major bleeding event will be censored at the last visit date with evaluation. Additional information on the Bleeding CRF will also be summarized and/or listed.

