
[figure not shown]
PROTOCOL SYNOPSIS *Continued*

Treatment Groups	
There will be 3-dose cohorts that will run concurrently. Subjects will be stratified based on the diagnosis of documented atrial fibrillation and then randomized to 1 of 3 dose cohorts in a 1:1:1 ratio (Cohort A, Cohort B, and Cohort C). Within each dose cohort, subjects will be randomized in a 3:1 ratio to receive subcutaneous treatment with either ISIS 416858 or placebo that is added to standard of care hemodialysis therapies as prescribed by their providers, including heparin.
 
Cohort A: Approximately 68 dialysis subjects will be randomized 3:1 to either 200 mg ISIS 416858 or placebo
 
Cohort B: Approximately 68 dialysis subjects will be randomized 3:1 to either 250 mg ISIS 416858 or placebo
 
Cohort C: Approximately 68 dialysis subjects will be randomized 3:1 to either 300 mg ISIS 416858 or placebo

Study Drug Dosage and Administration	
The SC Tolerability assessments using 0.9% sterile saline should be administered as two 0.75 ml noncontiguous injections on Study Days S-14 (\pm 3) and S-7 (\pm 3).
 
For Cohort A, B and C, the Sponsor will provide ISIS 416858 (200 mg/ml, 1.0 ml) and Placebo (1.0 ml). All doses are given by SC injection.
 
Study Drug will be administered SC post-dialysis at any time from when blood is being returned to the subject but must be within 2 hours (preferably within 15 minutes of dialysis conclusion) for a total of 26 consecutive weeks of treatment in all cohorts.
 
The injection volume will be 1.0 ml for Cohort A (200 mg), 1.25 ml for Cohort B (250 mg) and 1.5 ml for Cohort C (300 mg). Cohorts B and C will be administered Study Drug (ISIS 416858 or placebo) as 2 noncontiguous SC injections.

Rationale for Dose and Schedule Selection	Based on the PK/PD profile of ISIS 416858 in the previous Phase 1 (ISIS 416858-CS1) and Phase 2 (ISIS 416858-CS3 and ISIS 416858-CS4) studies, doses up to 300 mg of ISIS 416858 have demonstrated significant reduction in FXI activity and consequent anti-thrombotic effects without an increased bleeding risk.

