8. TREATMENT OF SUBJECTS

8.1 Study Drug Administration

Study Drng (ISIS 416858 or placebo) will be administered SC by trained personnel at the Study Center. Volumes to be administered are shown in Table 3. All doses of Study Drng will be administered after the completion of the hemodialysis treatment which can be while blood is returning to the patient but must be within 2 hours (preferably within 15 minutes of the conclusion of dialysis). Vials are for single use only. Please refer to the Study Drng Manual provided by the Sponsor (or designee) for more detailed instructions for Study Drng (ISIS 416858 or placebo) preparation and administration.

Table 3 Study Drug Dosing Information

Cohort	Volume to Administer	Number of Injections	Total Dose*
Cohort A (200 mg ISIS 416858 or placebo)	1.0 ml	1 of 1.0 ml	5200 mg ISIS 416858 or placebo
Cohort B (250 mg ISIS 416858 or placebo)	1.25 ml	1 of 0.75 ml and 1 of 0.5 ml	6500 mg ISIS 416858 or placebo
Cohort C (300 mg ISIS 416858 or placebo)	1.5 ml	2 of 0.75 ml	7800 mg ISIS 416858 or placebo

* Total dose of ISIS 416858 based on completed treatments for each cohort

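### Pooled placebo mixes one- and two-injection regimens, so local injection-site tables can place 200 mg below and 250/300 mg above placebo without any local drug effect

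*Combined protocol and SAP*

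**What the plan says.** **Regimen.** Protocol Table 3 (section 8.1) gives Cohort A one 1.0 mL injection per dose, Cohort B "1 of 0.75 ml and 1 of 0.5 ml", and Cohort C two of 0.75 mL. The Protocol Synopsis confirms that placebo is matched within cohort: "Cohorts B and C will be administered Study Drug (ISIS 416858 or placebo) as 2 noncontiguous SC injections".

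**Comparator.** SAP 2.1.1 states: "Patients who are placebo-treated will be pooled and analyzed as a single placebo group". SAP 2.3 adds: "Safety summary tables will be presented by treatment group and ISIS 416858 total". Neither section shows placebo by cohort or by injections per dose.

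**Local outcomes.** SAP 2.3.3.1 defines a per-subject percentage for local cutaneous reactions at the injection site (LCRIS), "where A=number of Study Drug injections with a LCRIS, and B=total number of Study Drug injections", and then the counting rule "Doses that are split across multiple Study Drug injections are counted as a single injection". It also summarises patients with any, moderate and severe LCRIS, and discontinuations for an injection-site event. SAP 2.3.3.3 says of bleeding: "Minor bleeding at the injection site will be summarized separately".

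**Flu-like reactions.** SAP 2.3.3.2 uses a percentage "where A=number of injections leading to flu-like reactions, and B=total number of injections" and does not say how a split dose is counted.

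**The concern.** In the active arms, the number of punctures and the volume are fixed by the dose. In the pooled placebo column they are a mixture. A reader who sets 200, 250 or 300 mg beside that column compares regimens that differ in needle sites and millilitres as well as in drug. For most outcomes this is harmless. For outcomes that arise at the injection site it is not, because an inert injection can cause them.

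Safety across the three doses is part of the primary objective (Protocol 1.1), and these tables are where local tolerability would be judged. The risk is that a difference produced by the way the dose is given is read as a drug effect. The trial already randomizes a matched control in each cohort, but the planned tables do not use it.

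**Working it through.** **1. The plan's own figures.** Volume × 200 mg/mL × 26 doses: 1.0 × 200 × 26 = 5200 mg; 1.25 × 200 × 26 = 6500 mg; 1.5 × 200 × 26 = 7800 mg. These match Table 3, so the volumes and injections per dose are read correctly.

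**2. Make-up of pooled placebo.** 204/3 = 68 per cohort; 3:1 gives 51 active and 17 placebo. Pooled placebo is 51 patients: 17 (one third) with one injection per dose and 34 (two thirds) with two.

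**3. No drug effect, equal risk p per puncture, independent sites.** The documents give no p, so a range is shown. A dose with a reaction at either site counts once. One injection: p. Two injections: 1 − (1 − p)². Pooled placebo: [p + 2(1 − (1 − p)²)]/3.

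| p | A | B = C | Pooled placebo | A / placebo | B, C / placebo |
|---|---|---|---|---|---|
| 0.1% | 0.10% | 0.20% | 0.17% | 0.600 | 1.200 |
| 0.5% | 0.50% | 1.00% | 0.83% | 0.601 | 1.199 |
| 1% | 1.00% | 1.99% | 1.66% | 0.602 | 1.199 |
| 2% | 2.00% | 3.96% | 3.31% | 0.605 | 1.198 |
| 5% | 5.00% | 9.75% | 8.17% | 0.612 | 1.194 |
| 10% | 10.00% | 19.00% | 16.00% | 0.625 | 1.188 |

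The ratios hardly move with p. The absolute gap between A and B/C does: 0.1 points at p = 0.1%, about 2 points at p = 2%.

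**4. Correlated sites.** With correlation ρ between the two sites of a dose, the two-injection risk is 2p − [p² + ρp(1 − p)]. At p = 2% it is 3.96% for ρ = 0, 2.98% for ρ = 0.5 and 2.00% for ρ = 1. At ρ = 1 the puncture-count artefact is gone.

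**5. Risk follows total volume instead.** Let h = −ln(1 − 0.02) per mL, with risk per dose 1 − exp(−hV). For V = 1.0, 1.25 and 1.5 mL this gives 2.00%, 2.49% and 2.99%. Pooled placebo is their mean, 2.49%. Ratios: 0.80, 1.00, 1.20.

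**6. Patient level.** Over 26 doses, with all punctures independent, any LCRIS is 1 − (1 − p)^26 in A and 1 − (1 − p)^52 in B and C. At p = 1%: 23.0%, 40.7%, pooled placebo 34.8%. At p = 2%: 40.9%, 65.0%, pooled placebo 57.0%. The split-dose rule plays no part here, yet the same pattern appears.

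**7. Does counting per injection site repair it?** Under step 3, yes: p everywhere. Under step 5, no: A 2.00%, B 1.25%, C 1.50%.

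**8. Does matched placebo repair it?** By cohort, yes under both models, since punctures and volume are the same on both sides. By injections per dose, fully under step 3. Under step 5 the two-injection placebo group averages (2.49 + 2.99)/2 = 2.74%, leaving ratios of 0.91 for B and 1.09 for C.

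**9. Flu-like percentage.** Take two doses with a reaction out of 26. Cohort A: 2/26 = 7.7%. Cohorts B and C: 2/26 = 7.7% if doses are the unit; 4/52 = 7.7% if both injections of a dose are attributed; 2/52 = 3.8% if only the denominator is counted in physical injections.

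**The case against.** Two punctures are part of the 250 and 300 mg regimens as given, so risk per dose is a legitimate quantity. LCRIS is narrow: reactions of at least moderate severity that last two days or more, or events that end treatment. The background rate may therefore be very low and the absolute gap about 0.1 points. The LCRIS and flu-like summaries are descriptive with no test named, so no type I error is at stake. The primary safety outcome is major plus clinically relevant non-major bleeding, and injection-site minor bleeding is already kept apart from the other bleeding events. Cohort-specific placebo columns are thin: one patient in 17 is 5.9 points, and at 0.1% per puncture Cohort A placebo (17 × 26 = 442 punctures) has a 0.999^442 ≈ 64% chance of no event.

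All of this stands as a limit on size and as a reason to add columns, not to replace the pooled one. It does not remove the point: if the regimen as given is the quantity of interest, the comparator should be the same regimen with placebo, and pooled placebo is not.

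Three stronger readings are tempting and not supported.

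- A reader might infer a spurious dose-response. Puncture count gives a single step with B equal to C. A graded pattern needs the volume mechanism, under which 250 mg sits level with placebo.
- A reader might blame the split-dose rule. Step 6 shows that the confounding is there without it, and step 7 that counting by site can distort in its own way.
- A reader might infer that the flu-like percentage favours the higher doses, or that the LCRIS and flu-like denominators have been interchanged. SAP 2.3.3.2 leaves the unit open, and two of the three readings in step 9 give no difference.

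**Conclusion.** The point holds for local injection-site outcomes: LCRIS, discontinuation for an injection-site event, and injection-site minor bleeding. Pooled placebo is not matched to any dose on punctures and volume, and nothing else in the SAP corrects this. With no local drug effect, the tables can show about 0.60 times placebo at 200 mg and 1.20 times at 250 and 300 mg (equal, independent risk per puncture), or about 0.80, 1.00 and 1.20 (risk proportional to volume). Both sets are conditional on an assumed mechanism. The first weakens as the two sites of a dose correlate, and the absolute size depends on a background rate that the documents do not give. The consequence is possible misreading of descriptive safety tables, not an invalid test. The flu-like percentage is a separate and minor ambiguity of unit.

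**What to change.** For the three local outcomes only, add to SAP 2.3.3.1 and 2.3.3.3 placebo columns beside the pooled one. Columns by cohort (about 17 each) match both punctures and volume. Columns by injections per dose (about 17 and 34) are larger, but leave a small volume difference within the two-injection group. State that each dose is read against its matched placebo, and that any overall active-versus-placebo contrast on these outcomes is stratified by cohort.

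Keep the LCRIS percentage per dose, and say that a dose with reactions at both sites counts once. Keep pooled placebo for all other outcomes.

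In SAP 2.3.3.2, apply the split-dose rule of 2.3.3.1 so that numerator and denominator are both doses.

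The cost is a few sentences and some table columns, with no change to trial conduct or data collection. The drawback is low precision in the small placebo columns, so they should be presented with counts and not over-read.

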2.3.3.2 Flu-like Reactions

Flu-like reactions (FLRs) will also be summarized using the MedDRA coding system, by preferred term.

Flu-like reactions are defined as either (A) flu-like illness or (B) Pyrexia or feeling hot or body temperature increased, plus at least two of the following: Chills, Myalgia, and Arthralgia, starting on day of injection or the next day.

Percentage of injections leading to flu-like reactions will be summarized using the descriptive statistics.

Percentage of the injections leading to flu-like reactions will be calculated as follows for each subject: (A/B)*100, where A=number of injections leading to flu-like reactions, and B=total number of injections.

2.3.3.3 Bleeding

Major bleeding (MB) is defined as one of the following:

1. Fatal bleeding
2. Symptomatic bleeding in a critical area or organ, such as intracranial, intraspinal, intraocular, retroperitoneal, intraarticular if in a major joint, or pericardial, or intramuscular with compartment syndrome
3. Clinically overt bleeding leading to transfusion of units of packed red blood cells or whole blood or a fall in hemoglobin of 20 g/L(1.24 mmol/L) or more within 24 hours

Clinically relevant non-major bleeding (CRNMB) is defined as overt bleeding not meeting the criteria for major bleeding but that resulted, for example, in medical examination, intervention, or had clinical consequences for a patient.

Minor bleeding:

All other acute clinically overt bleeding events not meeting the criteria for either major or clinically relevant non-major bleeding will be classified as minor. Minor bleeding will be further categorized as injection site and non-injection site bleeding events.

The incidence of any bleeding event after first dose of study drug will be summarized by treatment group for the Safety Population for all bleeding events except minor bleeding at the injection site. Minor bleeding at the injection site will be summarized separately. The summary will include the following outcomes:

- MB
- CRNMB
- Minor bleeding (Non-injection site and injection site events)
- Combination of MB and CRNMB (with either MB or CRNMB)

The cumulative rate of first major bleeding events after first dose of study drug will be displayed using Kaplan-Meier curves for the safety population. Patients without major bleeding event will be censored at the last visit date with evaluation. Additional information on the Bleeding CRF will also be summarized and/or listed.

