1.3 Planned Method of Analysis

1.3.J Safety and Tolerability Outcomes

The primary safety outcome is the combination of major bleeding (MB) and clinically-relevant non-major bleeding (CRNMB) during the treatment period (or early study termination).

The safety and tolerability of ISIS 416858 will be accessed by determining the incidence and severity of adverse events (AEs) and will be evaluated by reviewing:

- AEs (including venous thromboembolism (VTE) and bleeding events)
- Vital signs and weight
- ECG
- Physical examination
- Clinical laboratory tests
- Coagulation parameters
- Use of concomitant medications including transfusions

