- AEs that have onset dates after study termination date for the post-treatment evaluation period will be assumed to have occurred after the study period. If the onset of an AE is a partial date with only month or year available or complete missing, then similar approach as above will be used

The ESRD related adverse event is defined as TEAE with "Related", "Possible" relationship to ESRD. If the AE relationship to ESRD is missing or it has been defined as "Unlikely/remote", it will be considered as a Non-ESRD/Procedure-related AE.

All adverse event summaries will be restricted to treatment-emergent adverse events (TEAE).

The incidence of treatment-emergent adverse events will be summarized by treatment group and ISIS 416858 total, by MedDRA preferred term and system organ class for the followings:

- AE Overview
- AE Overview for ESRD/Procedure-related adverse events
- AE Overview for non-ESRD/Procedure-related adverse events
- TEAEs
- TEAE for ESRD/Procedure-related adverse events
- TEAE for non-ESRD/Procedure-related adverse events
- TEAEs potentially related to study drug. Potentially related is defined as "Related", "Possible", or missing relationship to study drug
- Serious TEAEs
- Serious TEAEs potentially related to study drug
- TEAEs resulting in permanently discontinuation of study drug
- Subjects with non-serious AE. The subjects with non-serious AE are those subjects having at least one non-serious adverse event, but no SAE.
- TEAE by maximum severity. At each level of patient summarization, a patient is classified according to the highest severity if the patient reported one or more events. Adverse events with missing severity will categorized as "Missing" for this summary. Event counts will also be provided for each level of severity.
- TEAEs potentially related to study drug by maximum severity

- Serious TEAEs potentially related to study drug by maximum severity

Events will be sorted by total incidence of each System Organ Class then by total incidence of each Preferred Term within each System Organ Class. For incidence counts, each patient will be counted only once within each Preferred Term and within each SOC. Percentages will be based on the number of patients in a particular treatment arm.

2.3.3 .J Local Cutaneous Reactions at the Injection Site

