1. OBJECTIVES

1.1 Primary Objectives

To evaluate the safety, pharmacokinetics (PK), and pharmacodynamics (PD) of ISIS 416858 (200, 250, and 300 mg once-weekly) as compared to placebo as assessed by FXI activity reduction in ESRD patients on hemodialysis;

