10.6.2 Safety Analysis

Treatment duration and amount of Study Drng (ISIS 416858 or placebo) received will be summarized by treatment group. Subject incidence rates of all AEs will be tabulated by the Medical Dictionary for Regulatory Activities (MedDRA™) system organ class, and by MedDRA™ term. Tables and/or narratives of treatment-emergent deaths, serious and significant AEs, including early withdrawals due to AEs, will also be provided.

All treatment-emergent AEs, all treatment-emergent AEs potentially related to Study Drng, all treatment-emergent serious AEs, and all treatment-emergent serious AEs potentially related to Study Drng (ISIS 416858 or placebo) will be summarized.

Laboratory tests to ensure subject safety including chemistly panel, complete blood count with differential, coagulation panel, complement etc., will be summarized by study visits for each treatment group. These safety variables will also be presented as change and percent change from Baseline over time after Study Drng (ISIS 416858 or placebo) administration, as appropriate.

Vital sign and ECG measures will be tabulated by treatment group. In addition, the number of subjects who experience abnormalities in clinical laboratory evaluations will be summarized by treatment group.

Incidence of bleeding events including the following will be tabulated by treatment:

- MB
- CRNMB
- Minor bleeding
- Combination of MB and CRNMB

Physical examination data will be provided in the data listing. Concomitant medications will be coded using World Health Organization (WHO) Drng dictionruy and summarized by treatment, ATC class and generic name.

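### No comparison with placebo, interval or follow-up-adjusted estimate is pre-specified for the primary safety outcome (MB or CRNMB), and its analysis window is not settled

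*Combined protocol and SAP*

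**What the plan says.** SAP 1.3.1 defines the outcome and its window: "The primary safety outcome is the combination of major bleeding (MB) and clinically-relevant non-major bleeding (CRNMB) during the treatment period (or early study termination"). Protocol 10.1.1 says the same. Protocol 1.1 and SAP 1.2.1 frame the objective as safety, PK and PD "as compared to placebo as assessed by FXI activity reduction in ESRD patients on hemodialysis". The protocol synopsis states the comparison with placebo without the FXI qualifier.

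For the analysis, SAP 2.3.3.3 says: "The incidence of any bleeding event after first dose of study drug will be summarized by treatment group for the Safety Population". The composite is one of the listed rows. Protocol 10.6.2 is no more specific: "Incidence of bleeding events including the following will be tabulated by treatment". For adverse events in general, SAP 2.3.3 adds: "Percentages will be based on the number of patients in a particular treatment arm".

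The only time-to-event output is for one component: "The cumulative rate of first major bleeding events after first dose of study drug will be displayed using Kaplan-Meier curves for the safety population". Its censoring rule is: "Patients without major bleeding event will be censored at the last visit date with evaluation".

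Elsewhere the SAP is comparative. Section 2.4 compares FXI and aPTT with pooled placebo, and gives clotting a rank test, exact intervals, odds ratios, 95% CIs and baseline-adjusted models. Section 2.6 compares URR and Kt/V with pooled placebo.

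**The concern.** A primary safety outcome in a placebo-controlled trial should come with an estimate of the difference from placebo and a statement of its uncertainty. Here it has neither, while pharmacodynamic outcomes and dialysis adequacy have planned comparisons.

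The risk is misreading. The protocol's own background (2.2, 2.3.3.3 and 2.4) already describes small earlier studies as showing no increase in bleeding. A table of similar percentages from this trial invites the same sentence, with nothing beside it to show which increases remain possible.

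Two further gaps affect the number itself. A percentage of all dosed subjects counts someone who leaves early without an event as event-free for the whole period. And since the text does not fix the window, two analysts could produce different primary results from the same data.

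**Working it through.** **Arm sizes.** SAP 1.1 and the protocol synopsis give about 204 subjects, 68 per cohort, randomised 3:1. So 68 × 3/4 = 51 per dose and 68 × 1/4 = 17 placebo per cohort. SAP 2.1.1 pools placebo: 3 × 17 = 51. Total active is 3 × 51 = 153. The plan gives no power, bleeding rate or margin to reproduce; SAP 2.1.3 says the sample size has no statistical rationale. The event and loss rates below are therefore assumptions.

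**Precision at equal observed rates.** Newcombe interval for a difference, built from the Wilson limits (l, u) of each proportion p (1 = active, 2 = placebo):

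upper = d + √[(u₁ − p₁)² + (p₂ − l₂)²]; lower = d − √[(p₁ − l₁)² + (u₂ − p₂)²].

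For 3/51, p = 0.0588, with Wilson limits 0.0202 and 0.1592. With 3/51 in both arms, d = 0 and the half-width is √(0.1004² + 0.0386²) = 0.108.

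| Observed rate, both arms | One dose v placebo (51 v 51) | Total active v placebo (153 v 51) |
|---|---|---|
| 5.9% (3/51; 9/153) | -10.8 to +10.8 points | -10.4 to +6.3 |
| 9.8% (5/51; 15/153) | -12.5 to +12.5 | -11.8 to +8.0 |
| 15.7% (8/51; 24/153) | -14.4 to +14.4 | -13.3 to +10.0 |

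A doubling adds as many points as the placebo rate. Set against the observed placebo rate, it lies inside the per-dose interval at 5.9% (5.9 < 10.8) and at 9.8% (9.8 < 12.5), but not at 15.7% (15.7 > 14.4). For total active it lies inside at 5.9%, only just (5.9 < 6.3), and outside at 9.8% (9.8 > 8.0).

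**Bias from unequal time on study.** Assume a true 26-week risk of 10% in both arms, a constant hazard, and that those who leave do so at Week 8. Risk by Week 8 is 1 − 0.9^(8/26) = 3.19%. With a fraction d leaving, the crude percentage is (1 − d) × 10% + d × 3.19%:

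- 10% leave (placebo): 9.32%
- 20% leave (active): 8.64%, ratio 8.64/9.32 = 0.93
- 30% leave (active): 7.96%, ratio 7.96/9.32 = 0.85

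The shift is 0.7 to 1.4 points. The sampling standard error of a per-dose difference at 10% is √(2 × 0.1 × 0.9/51) = 5.9 points. Spreading the losses evenly over 26 weeks (exponential drop-out, 20% to 40% active against 10% placebo) gives crude ratios of 0.95 to 0.83.

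**Window, side by side.**

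- SAP 1.3.1 and protocol 10.1.1: the treatment period, or early study termination.
- Protocol 3.4.2: that period ends with the last injection on Day 176, or at early study termination.
- SAP 2.3.3.3: from first dose, with no end stated.
- Protocol 8.5.3: bleeding is evaluated up to Day 260.
- SAP 2.1.1: a separate on-treatment analysis is optional, with no method.

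Read literally, the SAP table could include 260 − 176 = 84 days of post-treatment events that the outcome definition excludes.

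**The case against.** The strongest reply is that nothing is lost. The trial is randomised, double-blind and placebo-controlled, and the composite is tabulated by arm in all dosed subjects, so anyone can compute a crude difference and interval from the counts. That is right. A reader might infer that the trial cannot support any conclusion on bleeding against placebo; the documents do not support that. The defect is that the comparison is not pre-specified.

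Second, the width of the intervals comes from the sample size, which the documents openly say has no statistical basis. Printing an interval shows the imprecision and does not reduce it. This also stands.

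Third, follow-up may not differ much. Protocol 3.4, 8.6 and 8.7 encourage subjects who stop drug to stay, and SAP 2.3.1 summarises treatment duration and time on study by group, so an imbalance would be visible. This limits unequal time on study, though not unequal time on drug. The bias calculated above is small beside sampling error.

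Three other inferences should be avoided. Clotting is not a secondary endpoint that outranks bleeding: it is listed as a pharmacodynamic outcome and its measurement is called exploratory. The Kaplan-Meier rule does not censor all deaths, because fatal bleeding is itself MB; only deaths without MB are censored. And the objective's wording ties the comparison to FXI activity reduction, so its application to bleeding is clearest in the synopsis.

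**Conclusion.** The point holds as a gap in pre-specification. For MB or CRNMB the plan has no contrast with placebo, no interval, no follow-up-adjusted estimate and no time-to-event display. MB alone has a curve. The analysis window disagrees with the outcome definition.

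The main consequence is interpretive. At an assumed 6% to 10% event rate, equal percentages for a dose and placebo leave increases of about 11 to 12 points unexcluded, which includes a doubling. At about 16% a doubling would be excluded, so this conclusion depends on the rate. The follow-up bias is secondary: 0.7 to 1.4 points under the Week 8 scenarios, which rest on assumed losses. The documents give no death rate either, so the effect of censoring non-bleeding deaths cannot be sized.

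**What to change.** In SAP 2.3.3.3, for first MB or CRNMB:

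1. State the window of the primary analysis, in line with the treatment-period definition in SAP 1.3.1. Say how events after early stopping of drug are counted, and report events through Day 260 separately.
2. Report the risk difference from pooled placebo with a 95% CI for each dose and for ISIS 416858 total. Name the interval method, and say whether the difference uses crude proportions or cumulative incidence at the end of the window.
3. Add a time-to-first-event curve for the composite and cumulative incidence by arm with 95% CIs. Treat non-bleeding deaths as a competing event or, if they are few, do so in a sensitivity analysis.

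No hypothesis test and no larger sample is needed. The data are already collected, so the cost is SAP wording, one table and one figure. The downside is that the intervals will be wide and the safety statement less favourable than bare percentages suggest. Pooling the doses helps modestly: √(1/153 + 1/51) ÷ √(2/51) = 0.82, a standard error about 18% smaller than for one dose.
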